Evaluation of Gingival Crevicular Fluid and Saliva SOST and TWEAK, Gingival Crevicular Fluid RANKL and OPG Levels in Smokers and Non-smokers with Periodontitis

14.09.2023

Study Protocol

Study Population

Participants who applied to Gazi University Faculty of Dentistry Department of Periodontology for periodontal treatment or control, who were systemically healthy and who agreed to participate in the study were included in the study.

Participants who agreed to participate in the study were evaluated clinically and radiologically and diagnosed in accordance with the Classification of Periodontal and Peri-implant Diseases and Conditions 2017 Workshop criteria. Accordingly, the individuals who will take part in the study are; Systemically healthy, non-smoking periodontitis group (Group 1, number = 26), systemically healthy, smoker periodontitis group (Group 2, number = 26) and systemic and periodontal healthy group (Group 3, number = 26).

Clinical examination

In order to evaluate the clinical conditions of the participants in the study; Plaque index, gingival index, percentage of bleeding on probing, pocket depth and clinical attachment loss were recorded for each tooth from four regions (mesiobuccal, buccal, distobuccal, lingual/palatinal) using the Williams probe. Clinical indices were measured and recorded by a single calibrated investigator. Stages and grades in the classification of periodontitis patients; Radiographic bone loss was determined according to the parameters of pocket depth, amount of attachment loss, number of teeth lost due to periodontitis, bone loss%/age and case phenotype.

GCF collection

GCF samples were collected from all individuals participating in the study with paper strips. GCF samples were placed in 2 Eppendorf tubes with paper strips in fours. After the tubes were closed with parafilm, they were stored at -30°C until ELISA examination to determine cytokine levels.

Saliva collection

Total saliva samples were collected from the individuals participating in the study by spitting the saliva accumulated at the bottom of the mouth into a test tube every 60 seconds for a period of 5 minutes. The collected saliva samples were stored at -30°C until ELISA examination to determine cytokine levels.

Laboratory analysis

Gingival crevicular fluid and saliva samples were examined by the ELISA method in accordance with the manufacturer's instructions (Bioassay Technology Laboratory Human Sklerostin SOST BT-LAB ELISA Kit, Bioassay Technology Laboratory Human Osteoprotegerin OPG OPG BT-LAB Kit ELISA kit, Bioassay Technology Laboratory Human Tumour necrosis related weak inducer of apoptosis, TWEAK BT LAB ELISA kit, Human Receptor Activator of Nuclear Factor Kappa B Ligand RANKL BT-LAB ELISA kit) to determine biomarker levels.

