**14.09.2023**

Statistical analyzes were performed with Jamovi (Version 2.3.24.0) and JASP (Version 0.17.1) programs, and 0.05 (p-value) was taken into account as the significance level in statistical analyses.

While summarizing the study data, "median, minimum and maximum" values were added to the table depending on the distribution for continuous (numerical) variables. Categorical variables were presented as numbers. Normal distribution of numerical variables was evaluated using Shapiro-Wilk, Kolmogorov-Smirnov and Anderson-Darling tests.

To compare categorical variable differences between groups, Pearson Chi-Square test was used in 2x2 tables with expected number of observations being 5 or more, and Fisher's Exact Test was used in tables with expected number of observations below 5. Fisher Freeman Halton test was used in RxC tables with expected number of observations below 5.

When two independent groups were compared, Mann Whitney U test was used in cases where numerical variables were not normally distributed.

When multiple independent groups were compared, the Kruskal-Wallis H test was used when numerical variables were not normally distributed. Differences between groups were evaluated with the Dwass-Steel-Critchlow-Fligner test.

In examining the relationships between numerical variables, Spearman's Rho correlation coefficient was used in cases where the variables were not normally distributed.

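### Must the plan define GCF levels more closely and add a RANKL/OPG ratio to guard against a fluid-yield difference between groups?

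*Protocol*

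**What the plan says.** The Protocol title names "Gingival Crevicular Fluid RANKL and OPG Levels in Smokers and Non-smokers with Periodontitis", and also SOST and TWEAK in both GCF and saliva. Under GCF collection, "GCF samples were collected from all individuals participating in the study with paper strips", and "GCF samples were placed in 2 Eppendorf tubes with paper strips in fours". After sealing, "they were stored at -30°C until ELISA examination to determine cytokine levels". Under Laboratory analysis, "Gingival crevicular fluid and saliva samples were examined by the ELISA method", following the kit makers' directions. Neither section states a sampling time for GCF, a strip volume, an elution volume, a unit, a normalisation, or which tube served which assay. Saliva, by contrast, has a stated five-minute collection.

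Study Population sets three groups of 26; the third is the "systemic and periodontal healthy group (Group 3, number = 26").

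On analysis, the SAP says "When multiple independent groups were compared, the Kruskal-Wallis H test was used" for data that are not normally distributed, and "Differences between groups were evaluated with the Dwass-Steel-Critchlow-Fligner test". It also provides Mann-Whitney tests for two groups and Spearman correlation. It names no biomarker. A RANKL/OPG ratio is therefore neither defined nor excluded.

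**The concern.** What comes off a strip is fluid yield multiplied by concentration. If nobody divides by yield, a group comparison of the raw result mixes the two. The groups here are defined by periodontal disease and smoking, so a yield difference between them cannot be ruled out from the documents. Two errors would then be possible for a reader who thinks in concentrations: a difference between periodontitis and health that is only a difference in fluid, or a lower yield in smokers that hides a higher concentration.

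RANKL and OPG are both assayed in GCF, so their ratio looks like a cheap remedy. A yield factor common to both cancels, and no new samples are needed.

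**Working it through.** There is no figure in the plan to reproduce. The documents give no effect size, SD, power or sample-size calculation.

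**Inputs from the documents.** n = 26 in each of three groups (Protocol, Study Population); significance level 0.05, Kruskal-Wallis and Dwass-Steel-Critchlow-Fligner (DSCF) (SAP).

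**Assumptions, not in the documents.** Log-SD of concentration 0.7 (range 0.5 to 1.0); log-SD of yield 0.4 (range 0.2 to 0.8); yield ratios as shown; RANKL and OPG log-concentrations independent unless a correlation ρ is given. The DSCF critical value for three groups is |z| = 2.3437.

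**Step 1: the model.** Let V be yield and c concentration. Then log(RANKL) = log V + log c_R and log(OPG) = log V + log c_O. Subtracting, log(RANKL/OPG) = log c_R − log c_O, and V drops out if it is the same for both. The planned tests use ranks, so the ratio and its logarithm give the same p-value.

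**Step 2: how far yield alone could mislead.** True concentrations equal, simulated rejection rates:

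| Comparison on RANKL | Yield ratio | Rejects |
|---|---|---|
| Kruskal-Wallis, both periodontitis groups vs healthy | 1.0 / 1.25 / 1.5 / 2 | 5% / 15% / 41% / 87% |
| DSCF, smokers vs non-smokers with periodontitis | 1.0 / 0.9 / 0.8 / 0.7 / 0.6 | 2% / 3% / 8% / 19% / 42% |

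At 1.5 times the healthy yield, the Kruskal-Wallis figure runs from 25% to 61% over concentration log-SD 1.0 to 0.5, and from 25% to 50% over yield log-SD 0.8 to 0.2. A 10% lower yield in smokers changes almost nothing. These are false positives only for a statement about concentration. For a statement about amount they are correct detections.

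**Step 3: when the ratio protects.** With a shared group-level shift it stays at about 5% (Kruskal-Wallis) and 2% (DSCF). This holds for separate tubes too, provided both tubes carry the same shift. It does not hold otherwise:

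- Separate tubes, with the shift in the RANKL tube only: DSCF rejects in about 5%, 10% and 20% at smoker yields of 0.8, 0.7 and 0.6.
- Second tube carries only the square root of the shift (concentration log-SD 0.5): Kruskal-Wallis rejects in 12%, 25% and 57% at 1.5, 2 and 3 times the healthy yield.
- Additive assay background in one marker (concentration log-SD 0.5): 10–17%, 17–39% and 30–68% at the same three yields.

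**Step 4: what the ratio costs or gains.** Take a true doubling of RANKL concentration in smokers at equal yield; ln 2 = 0.693.

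- RANKL alone: SD = √(0.7² + 0.4²) = √0.65 = 0.806; standardised shift 0.693/0.806 = 0.860.
- Ratio, same tube: variance 2 × 0.49 × (1 − ρ). At ρ = 0, SD = √0.98 = 0.990 and the shift is 0.700.
- Ratio, separate tubes: add 2 × 0.16 = 0.32. At ρ = 0, SD = √1.30 = 1.140 and the shift is 0.608.

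Simulated DSCF power:

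| ρ | RANKL alone | Ratio, same tube | Ratio, separate tubes |
|---|---|---|---|
| −0.3 | 72% | 39% | 31% |
| 0 | 72% | 51% | 39% |
| 0.3 | 72% | 69% | 50% |
| 0.6 | 72% | 92% | 67% |

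At equal yield the two variances match when 0.98(1 − ρ) = 0.65, so ρ = 0.34 (same tube), or when 0.98(1 − ρ) + 0.32 = 0.65, so ρ = 0.66 (separate tubes). If smokers yield less, RANKL alone falls (at ρ = 0: 55%, 35% and 17% at yields of 0.9, 0.8 and 0.7) and the ratio does not. The yield at which the ratio overtakes RANKL therefore moves with ρ and the tube layout, neither of which the documents give. If both markers double in smokers, the ratio rejects in only 5% (Kruskal-Wallis), which is the chance rate.

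**The case for a change.** The best case for a change is that it is nearly free. Stating the unit, whether strip volume was recorded and which tube was used takes a few lines, and the ratio is one derived variable from results in hand. Without those lines a reader cannot tell amount from concentration, and the rates in Step 2 are large if the yield difference is 1.5-fold or more. The cancellation is exact under its condition.

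The first part stands as a matter of reporting: a paper from this study should say what its GCF values are. It does not show a fault in the planned analysis. Kruskal-Wallis and DSCF compare whichever quantity was measured, and they compare it validly. The text does not establish that values were left unnormalised; a volume may have been read, and the kit directions may fix the unit. It is also an inference that RANKL and OPG are tested only separately, because the SAP names no marker and a ratio is itself a numerical variable to which its tests would apply.

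The second part is weaker. The ratio is a different quantity from the marker levels in the title. It cannot show which marker moved, misses parallel changes and leaves SOST and TWEAK untouched. The SAP is written in the past tense, so a ratio added now might be exploratory only. A blanket relabelling of all GCF results as total amount could also be wrong, since that label needs a known elution volume, which is not stated.

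**Conclusion.** No change to the plan. The undefined unit, volume and tube allocation are missing detail, to be filled when results are reported: give the quantity as measured, call it total amount only if the elution volume is known and fixed, and do not read a group difference as one in concentration unless volume was recorded. None of this alters a planned test or its result.

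The possible distortion ranges from negligible (3% against 2% for a 10% lower smoker yield) to large (87% against 5% for a doubled periodontitis yield). It arises only if values are unnormalised, yields differ and the results are read as concentrations. The documents establish none of these, and every spread and yield above is assumed. A RANKL/OPG ratio is a reasonable optional extra, but its validity depends on a shared multiplicative shift with no additive background. Its power for a doubled RANKL runs from 31% to 92% depending on tube layout and correlation, against 72% for RANKL alone at equal yield. That is too uncertain a gain to require it.

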**14.09.2023**

Statistical analyzes were performed with Jamovi (Version 2.3.24.0) and JASP (Version 0.17.1) programs, and 0.05 (p-value) was taken into account as the significance level in statistical analyses.

While summarizing the study data, "median, minimum and maximum" values were added to the table depending on the distribution for continuous (numerical) variables. Categorical variables were presented as numbers. Normal distribution of numerical variables was evaluated using Shapiro-Wilk, Kolmogorov-Smirnov and Anderson-Darling tests.

To compare categorical variable differences between groups, Pearson Chi-Square test was used in 2x2 tables with expected number of observations being 5 or more, and Fisher's Exact Test was used in tables with expected number of observations below 5. Fisher Freeman Halton test was used in RxC tables with expected number of observations below 5.

When two independent groups were compared, Mann Whitney U test was used in cases where numerical variables were not normally distributed.

When multiple independent groups were compared, the Kruskal-Wallis H test was used when numerical variables were not normally distributed. Differences between groups were evaluated with the Dwass-Steel-Critchlow-Fligner test.

In examining the relationships between numerical variables, Spearman's Rho correlation coefficient was used in cases where the variables were not normally distributed.

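### Three non-randomised groups are compared only with unadjusted tests, so an age or sex imbalance could be read as an effect of periodontitis or smoking

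*SAP*

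**What the plan says.** The protocol's Study Population section recruits people attending one periodontology department "for periodontal treatment or control, who were systemically healthy and who agreed to participate in the study were included in the study". Two groups are described as "Systemically healthy, non-smoking periodontitis group (Group 1, number = 26), systemically healthy, smoker periodontitis group (Group 2, number = 26"), and the third as the "systemic and periodontal healthy group (Group 3, number = 26"). Membership follows from diagnosis and smoking status. No randomisation, matching rule, age range or sex balance is described, and no smoking status is given for Group 3.

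Age appears once, under Clinical examination, within the staging and grading of periodontitis patients: "number of teeth lost due to periodontitis, bone loss%/age and case phenotype". Sex appears nowhere.

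For three-group comparisons the SAP states "When multiple independent groups were compared, the Kruskal-Wallis H test was used when numerical variables were not normally distributed", followed by "Differences between groups were evaluated with the Dwass-Steel-Critchlow-Fligner test". The other tests it names are Mann-Whitney U, Pearson chi-square, Fisher's exact, Fisher-Freeman-Halton and Spearman's rho. It names no regression, ANCOVA, stratified analysis or partial correlation, and no test for normally distributed variables.

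The title sets the outcomes: "Evaluation of Gingival Crevicular Fluid and Saliva SOST and TWEAK, Gingival Crevicular Fluid RANKL and OPG Levels in Smokers and Non-smokers with Periodontitis". That is four biomarkers in gingival crevicular fluid and two in saliva, six in all.

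**The concern.** When groups are formed by disease and habit, nothing in the design balances age or sex. If either differs between groups and is related to a biomarker, an unadjusted rank test responds to it exactly as it would to a group effect. A reader who wants to link a difference to periodontitis (Group 1 v Group 3) or to smoking (Group 1 v Group 2) needs to know whether it remains at the same age and sex. The imbalance can work either way, creating a difference or concealing one.

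A related gap affects the periodontitis contrast. Group 1 v Group 3 isolates periodontitis only if Group 3 are non-smokers, and the protocol does not say so.

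Disease severity is deliberately not called a confounder here. It defines periodontitis against health, and it may lie on the path from smoking to the biomarker.

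**Working it through.** **Inputs from the documents.** 26 per group, three groups, significance level 0.05 (taken as two-sided). The documents give no effect size, SD, power, age distribution or sex split, so there is no figure of the plan's own to reproduce.

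**Assumed inputs.** Age gap of Group 3 below Groups 1 and 2: 0, 0.5, 1.0 or 1.5 SD. Age–biomarker correlation r: 0.2, 0.3 or 0.4. Normal errors and a linear age effect. Levels are generated as r × age + √(1 − r²) × error, with no group term, so an age gap shifts the group mean by r × gap (for example 0.3 × 1.0 = 0.30 SD).

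**Scale.** The pairwise difference detectable with 80% power is (1.960 + 0.842) × √(2/26) = 0.78 SD.

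**Pairwise threshold.** The large-sample Dwass-Steel-Critchlow-Fligner (DSCF) critical value is z = 3.314/√2 = 2.344, a nominal 1.9% per pair.

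**False positives from an age gap** (20,000 simulated trials per cell; entries are for gaps of 0 / 0.5 / 1.0 / 1.5 SD):

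| r | Kruskal-Wallis, % | DSCF Group 1 v 3, % |
|---|---|---|
| 0.2 | 4.9 / 6.2 / 9.9 / 16.5 | 1.8 / 2.4 / 4.6 / 9.0 |
| 0.3 | 5.1 / 7.4 / 16.9 / 33.9 | 1.8 / 3.2 / 9.0 / 20.5 |
| 0.4 | 5.1 / 9.9 / 27.2 / 55.7 | 1.8 / 4.7 / 16.0 / 37.8 |

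Rank ANCOVA on group, age and sex (2-df group test, 73 residual df) rejects 5.0–5.5% in all these cells. Its Tukey-adjusted Group 1 v 3 contrast rejects 1.9–2.2%.

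**False positives from sex alone** (10,000 trials per cell). With 80% male in Group 2 v 40% elsewhere and a 0.5 SD sex effect, Kruskal-Wallis rejects 9.2% and DSCF Group 1 v 2 rejects 4.4%. With 75% v 50% and a 0.3 SD effect the figures are 5.5% and 2.2%, almost no inflation.

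**Masking** (10,000 trials per cell). Take a true 0.8 SD difference for Group 3, opposed by the age gap, with r = 0.3. Kruskal-Wallis power falls from 82% with no gap to 62, 40 and 22% at gaps of 0.5, 1.0 and 1.5 SD. ANCOVA keeps 81, 76 and 66%.

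**Would a baseline test give enough warning?** Power to detect a 0.5 SD age gap with 26 v 26 is Φ(0.5/√(2/26) − 1.96) = Φ(−0.157) = 44%. For 70% v 50% male it is about 31%. A non-significant baseline comparison would not establish balance.

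**Price of adjusting.** Residual df fall from 78 − 3 = 75 to 78 − 5 = 73. With no imbalance and no age relation, power for a 0.8 SD difference is 81.2% (ANCOVA) v 82.0% (Kruskal-Wallis). For the Group 1 v 3 contrast, the variance ratio is about 1 + (gap² + 2/26) × 13/73 for age, plus (2/26) × 13/73 for chance sex imbalance. This gives 1.03, 1.07, 1.21 and 1.43 at gaps of 0, 0.5, 1.0 and 1.5 SD. The standard error therefore rises about 4, 10 and 20% at the three non-zero gaps.

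**Robustness of ANCOVA under the null.** With t(3) errors it rejects 4.7–5.8%. With four curved age shapes it rejects 4.7–5.6% at gaps up to 1.0 SD and 5.0–6.8% at 1.5 SD, where Kruskal-Wallis over the same curved settings ranged from 6 to 74%. At 1.5 SD the two age distributions overlap by only 2Φ(−0.75) = 45%, so the adjusted result leans on the model.

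**The case against.** The strongest reply is that neither document claims a cause. The title promises only an evaluation of levels, and the planned tests answer that validly for the groups as recruited. This is right as far as it goes. It makes cautious wording part of the remedy, but it does not help a reader who wants to know why the levels differ.

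The magnitude is wholly assumed, and the striking rates need a 1.5 SD gap with r = 0.4. At 0.5 SD and r = 0.2–0.3, Kruskal-Wallis rejects only 6.2–7.4%, and a moderate sex imbalance does almost nothing. This stands: material bias is possible, not shown. Nor does silence prove that no matching was done, since the protocol is brief and part of the SAP is not in the text available here. The SAP's categorical and rank tests could also be used to describe sex and age balance. Describing balance is not adjusting for it, however, and neither variable is named.

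The adjusted model has its own weak point. If the age slope is 0.3–0.4 in the periodontitis groups and zero in controls, with equal group means, rank ANCOVA rejects roughly 9–20% at gaps of 1.0–1.5 SD, while Kruskal-Wallis stays near 5%. Those are not false positives, because the groups do differ at a given age. A single adjusted difference summarises that situation poorly, though, so the slopes should be looked at.

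Finally, the SAP is written in the past tense. If the analysis is finished, the new models are later additions and must be labelled so.

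**Conclusion.** The concern holds. No randomisation or matching is described and no named test adjusts for age or sex, so the planned analysis cannot separate an imbalance in either from periodontitis or smoking. Under the assumed range of age gaps (0.5–1.5 SD) and correlations (0.2–0.4), the Kruskal-Wallis false-positive rate runs from 6.2 to 55.7% against a nominal 5%. DSCF Group 1 v 3 runs from 2.4 to 37.8% against a nominal 1.9%. If the groups turn out well balanced, or age and sex are unrelated to the biomarkers, adjustment will change little, but the documents give no means of knowing. This should be fixed. Confidence is medium, because the actual imbalance is unknown.

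**What to change.** 1. For each of the six biomarker-by-fluid outcomes, add an ANCOVA with group, age and sex on transformed levels. Choose rank or log once, before looking at results; the figures above are for ranks.
2. Use the 2-df group test, then multiplicity-adjusted pairwise contrasts, naming Group 1 v Group 2 for smoking and Group 1 v Group 3 for periodontitis. Report the planned rank tests alongside.
3. State whether the groups were matched. Tabulate age, sex and smoking status by group, including Group 3. Show biomarker against age by group, so that unequal slopes or poor overlap are visible.
4. Describe differences as associations. Use attachment loss or stage only in a labelled secondary model for Group 1 v Group 2, not as a confounder.
5. If the analysis is already complete, label the adjusted models as added afterwards.

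The cost is SAP wording, six models, two residual degrees of freedom and 0.8 points of power (82.0 − 81.2) when there is nothing to adjust for. Precision falls where ages differ, and some differences may shrink. The fix assumes that age and sex are recorded for all 78 participants, which is plausible but not stated. Age/sex adjustment does not resolve Group 3's smoking status, which has to be reported.

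### Should smokers and non-smokers be compared with Kruskal-Wallis-gated Mann-Whitney tests in place of the Dwass-Steel-Critchlow-Fligner procedure?

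*SAP*

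**What the plan says.** The SAP sets one threshold for everything: "0.05 (p-value) was taken into account as the significance level in statistical analyses". For more than two groups it states "When multiple independent groups were compared, the Kruskal-Wallis H test was used when numerical variables were not normally distributed", and the next sentence is "Differences between groups were evaluated with the Dwass-Steel-Critchlow-Fligner test". A separate paragraph covers the two-group case: "When two independent groups were compared, Mann Whitney U test was used in cases where numerical variables were not normally distributed". It does not say which variables or which pairs of groups that paragraph is for.

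The Protocol (Study Population) defines three groups of 26: non-smokers with periodontitis (Group 1), smokers with periodontitis (Group 2) and periodontally healthy participants (Group 3). The title names the contrast of interest and the measures: "Evaluation of Gingival Crevicular Fluid and Saliva SOST and TWEAK, Gingival Crevicular Fluid RANKL and OPG Levels in Smokers and Non-smokers with Periodontitis". That makes six measures, four in gingival crevicular fluid and two in saliva. Neither document gives an effect size, a standard deviation or a power calculation.

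**The concern.** All three groups provide samples, so the smoker versus non-smoker comparison falls naturally under the multiple-group paragraph and is tested as a DSCF pair. DSCF adjusts in a single step for all three pairs, which makes each pair stricter than 0.05.

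With exactly three groups that strictness is more than family-wise control requires. If all three distributions are equal, a Kruskal-Wallis gate at 0.05 protects every pair. If they are not all equal, at most one pair can still be equal, and a single test at 0.05 suffices for it. Gated Mann-Whitney is therefore a closed test with more power, and both component tests are already in the SAP. The apparent stake is lost power on the title contrast, with no extra participants needed to recover it.

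There is also a possible ambiguity. Someone could read the two-group paragraph as covering Group 1 versus Group 2, and the two tests can disagree.

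**Working it through.** **Inputs.** Level 0.05 (SAP; two-sided assumed, since sidedness is not stated); three groups of 26 (Protocol, Study Population); six measures (Protocol title). The shifts between smokers and non-smokers and the position of the healthy group are assumptions. There is no power figure in the plan to reproduce.

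**Per-pair level of DSCF.** The studentized range quantile is q(0.95; 3, ∞) = 3.3145. The critical |z| is 3.3145/√2 = 2.3437, so the two-sided per-pair level is 2 × (1 − Φ(2.3437)) = 0.0191.

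**Power, smokers versus non-smokers.** Monte Carlo with 26 per group, normal shifts, large-sample critical values and 40,000 replicates per scenario. Entries are gated Mann-Whitney versus DSCF, in %.

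| Shift (SD) | Healthy midway | Healthy equal to non-smokers | Healthy 1 SD beyond non-smokers |
|---|---|---|---|
| 0.5 | 29 vs 25 | 32 vs 25 | 40 vs 25 |
| 0.6 | 41 vs 38 | 46 vs 38 | 54 vs 38 |
| 0.8 | 67 vs 64 | 74 vs 64 | 78 vs 64 |
| 1.0 | 87 vs 85 | 92 vs 86 | 93 vs 86 |
| 1.1 | 93 vs 92 | 96 vs 92 | 97 vs 92 |

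The gain is 1 to 4 points with the healthy group midway, 4 to 10 with it equal to non-smokers, and 5 to 16 with it clearly separated. Rank tests are unchanged by a common monotone transformation, so the figures also hold for log-normal data with these shifts on the log scale. Heavier-tailed t(3) data gave gains of 1.9 to 15.5 points. Running DSCF only after a significant Kruskal-Wallis test changes its power by at most 1.4 points, so the loss comes from the DSCF adjustment itself.

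**False positives** (100,000 replicates per scenario).
- All three groups equal, any pair declared different: DSCF 4.7%, gated 4.8%.
- Only the healthy group differs, smoker contrast declared: DSCF 1.8% and gated 4.2% when the healthy group is 0.5 SD away; 1.7% and 4.8% at 1 SD or more.
- Across six measures, if independent: DSCF 1 − (1 − 0.0174)^6 = 10.0%; gated 1 − (1 − 0.048)^6 = 25.6%. If perfectly correlated, the figures stay at about 1.7% and 4.8%.
- Equal centres but unequal spread in smokers and non-smokers, healthy group well separated: gated about 5.6% at an SD ratio of 2 and 6.7% at a ratio of 3; DSCF 2.2% and 2.7%.

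**Where the gate costs power.** With the healthy group midway, about 0.5 to 1.4% of data sets are significant by DSCF but blocked by Kruskal-Wallis.

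**Disagreement between DSCF and an ungated Mann-Whitney test** (p between 0.019 and 0.05): 14.7, 16.2, 13.9, 7.6 and 4.6% of data sets at 0.5, 0.6, 0.8, 1.0 and 1.1 SD.

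**The case for a change.** The strongest case for a change is that the arithmetic is right and the edit is cheap. At a shift of 0.8 SD, DSCF would need about 28, 31 or 34 per group, depending on where the healthy group lies, to match the gated test at 26. Per-biomarker family-wise error stays within 0.05 when the nulls are of identical distributions. The simultaneous intervals that closed testing gives up are not planned anyway. Naming one test would also remove a choice that could matter in roughly 5 to 16% of data sets.

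The efficiency gain is real, but it is not free. It comes from spending more of the error allowance on the contrast of interest, in a plan with no control across six measures. DSCF's strictness is the only slack there. The 5% ceiling also fails if smoking changes spread, and the documents give no data on that. The largest gains need a clearly separated healthy group and shifts of 0.5 to 0.8 SD. At 0.5 to 0.6 SD even the gated test reaches only 40 to 54%.

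The point about naming the test stands as a matter of detail. The SAP places DSCF directly after Kruskal-Wallis, and an analyst with three groups would apply it there and keep Mann-Whitney for comparisons that involve only two groups. If the two-group paragraph was instead meant for Group 1 versus Group 2, that contrast is already tested at 0.05 and no power is lost.

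**Conclusion.** No change is needed. DSCF is a valid procedure, and choosing it over gated Mann-Whitney is a fair trade-off. It gives up about 1 to 16 points of power under assumed shifts of 0.5 to 1.1 SD (1 to 4 if the healthy group lies midway). In return, false positives on the smoker contrast stay near 1.7% per biomarker, where the gated test allows about 4.8%. A statistician could reasonably prefer either.

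Timing points the same way. The SAP reports its analyses in the past tense, and so does most of the Protocol. If results have been seen, moving to a more powerful test for the main contrast would be a post-hoc switch, so DSCF should stay. The gated result could then be no more than a labelled sensitivity analysis, which leaves the main result as it is.

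This rests on DSCF being the test for Group 1 versus Group 2, which is the natural reading but not an explicit one; on the non-normal branch of the SAP applying; and on effect sizes that the documents do not supply.
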